#### **Early Withdrawal**

Subject discontinuation should be considered at the discretion of the principal investigator. The circumstances of any discontinuation have to be documented in detail. If possible, the evaluations planned for the end of study will be carried out at the time when the subject is withdrawn from the study.

Criteria for removal of subjects from the study will include:

#### Personal reasons

As stated in the Informed Consent Form, a subject may withdraw from the study for any reason at any time.

## Clinical judgment of physician

A subject may be withdrawn from the study if, in the opinion of the principal investigator, it is not in the subject's best interest to continue. This includes but is not limited to adverse events or serious adverse events related to the investigational product causing clinically significant illness; the need for prohibited concomitant medication; female subject who becomes pregnant during the course of the trial.

#### Protocol violation

Any subject found to have entered this study in violation of the protocol will be discontinued from the study at the discretion of the principal investigator. This will include any subject found to have been inappropriately enrolled (did not meet eligibility criteria). Subject non-compliance includes either not showing up for study visits, not taking investigational product as directed, or refusing to undergo study visit procedures. Subjects who are found to be less than 75% compliant with test article usage at any study visit will be withdrawn. Subjects who are found to be taking prohibited medications or supplements without the knowledge of the principal investigator will also be withdrawn. Any major protocol deviations (i.e., those that increase the risk to subjects and/or compromise the integrity of the study or its results) will result in subject discontinuation.

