# Endpoints

#### **Primary Endpoints**

- Change in mean trough FEV1 expressed as mililitres after 90 days of treatment
- Change in mean ACQ-7 scores after 90 days of treatment
- The threshold for change in ACQ-7 scores that is considered clinically important (MCID) is 0.5.

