# End of Treatment Visit (Visit 4 / Week 12/ Day 90) - CIC

Subjects will return the clinic on Day 90. Any remaining investigational product or empty packaging will be returned.

Study visit assessments will include:

- vitals signs, weight measurement
- review of concomitant therapies
- review of adverse events
- review of the diary card record
- symptoms examination
- compliance calculation
- Asthma Control Questionnaire
- Laboratory tests (basic hematology and chemistry)
- Exhaled nitric oxide (FENO) measurements, followed by
- Spirometry measurement (FEV1 and FVC)
- ECG

This visit will conclude the study.

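### Mandatory withdrawal from the study for low compliance or deviations leaves Day 90 data assured only for subjects who stay compliant, which may bias the single-arm change, probably upward

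*Protocol*

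**What the plan says.** The Protocol violation section has three firm triggers that act after enrolment:

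- **Low compliance:** "Subjects who are found to be less than 75% compliant with test article usage at any study visit will be withdrawn".
- **Undisclosed medication:** "Subjects who are found to be taking prohibited medications or supplements without the knowledge of the principal investigator will also be withdrawn".
- **Major deviations:** these "will result in subject discontinuation".

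The parent section, Early Withdrawal, introduces these rules as criteria for taking subjects out of the study, not merely off the product. For those who leave it provides that, where possible, "the evaluations planned for the end of study will be carried out at the time when the subject is withdrawn from the study". It plans no later contact.

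The Primary Endpoints are the change in trough FEV1 after 90 days and "Change in mean ACQ-7 scores after 90 days of treatment". The Secondary Endpoints (FeNO, eosinophils, IgE) use the same time point.

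The visit lists for Day 30 and Day 60 include the ACQ and FeNO but no spirometry. After screening, a new spirometry measurement is listed only at the End of Treatment Visit, where a "compliance calculation" is also listed.

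**The concern.** Whether a subject has a Day 90 value depends on what that subject does after starting the product. People who feel no benefit, tolerate the capsules poorly or turn to other medicines may be more likely to fall below 75% or break a medication rule. If so, those with Day 90 data are a favourable selection, and a single-arm, open-label study has no comparison group in which this would show.

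The matter belongs in the protocol because it concerns data collection. A statistical analysis plan can decide who is analysed and how gaps are handled, but it cannot recover measurements that were never taken. At stake is whether the mean change describes everyone who started the product or mainly those who kept taking it. The sample is also small, so a few removals matter.

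**Working it through.** **Step 1. What exists for a subject removed at Day 30 or Day 60**

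| Outcome | Listed at Day 30 and Day 60 | If removed there | Day 90 value planned? |
|---|---|---|---|
| ACQ-7 | yes | value(s) up to removal | no |
| FeNO | yes | value(s) up to removal | no |
| FEV1 | no | only if the withdrawal evaluation takes place | no |

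A withdrawal evaluation at Day 30 also precedes the dose escalation listed at that visit, so it does not stand in for a change after 90 days.

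**Step 2. Formula.** Let w be the share removed, dC the mean improvement in completers, and dW the mean improvement that removed subjects would have shown at Day 90.

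- All-subject mean = (1 − w) × dC + w × dW
- Completer mean minus all-subject mean = w × (dC − dW)

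**Step 3. Inputs.** The planned size is 17 (Study Design and Sample Size). The protocol gives no derivation for it, so there is no stated figure to reproduce. For scale I set dC at 0.50 for ACQ-7, since "The threshold for change in ACQ-7 scores that is considered clinically important (MCID) is 0.5", and at 200 ml for FEV1, the absolute part of the protocol's threshold. The number removed and dW are assumptions, because the protocol gives neither.

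**Step 4. Removed subjects unchanged (dW = 0), 17 enrolled**

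| Removed | ACQ-7 all-subject mean | Overstatement | FEV1 all-subject mean (ml) | Overstatement (ml) |
|---|---|---|---|---|
| 1 | 0.50 × 16/17 = 0.47 | 0.03 | 188 | 12 |
| 2 | 0.50 × 15/17 = 0.44 | 0.06 | 176 | 24 |
| 3 | 0.50 × 14/17 = 0.41 | 0.09 | 165 | 35 |
| 5 | 0.50 × 12/17 = 0.35 | 0.15 | 141 | 59 |

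**Step 5. Other values of dW, 17 enrolled**

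- Equal response (dW = dC): the bias is 0 for any number removed.
- Better response in removed subjects (dW = 0.75): 0.25 × 1/17 = 0.01 to 0.25 × 5/17 = 0.07 understatement on ACQ-7.
- Worsening in removed subjects (dW = −0.25): 0.75 × 1/17 = 0.04 to 0.75 × 5/17 = 0.22 overstatement.
- FEV1 with 5 removed: from 5/17 × (200 − 250) = −15 ml to 5/17 × (200 + 100) = +88 ml.

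**Step 6. If the size is 10.** The Study Population section gives 10 subjects, which must be reconciled with 17. With 10 enrolled and dW = 0, the ACQ-7 all-subject mean is 0.45, 0.40, 0.35 or 0.25 with 1, 2, 3 or 5 removed.

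**Step 7. Precision.** If removed subjects contribute no value, the 95% confidence half-width in SD units is t/√n. This is 0.51 with 17 and 0.64 with 12, and 0.635/0.514 = 1.24, so it is 24% wider.

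**Step 8. Compliance denominator.** The first-period regimen in the Baseline section can be read as 2 or 4 capsules a day. Sixty capsules in 30 days is then 60/60 = 100% or 60/120 = 50%, and the second falls below the withdrawal threshold. The wording must be reconciled before the rule can be applied consistently.

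**The case against.** The other side has several sound points, and each limits what can be claimed.

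- **Analysis restricted to completers.** A reader might infer that withdrawn subjects are dropped from the analysis. The protocol does not say so. It defines no analysis set, and the statistical analysis plan, which is not at hand, may do so. The point here is about which data get collected.
- **Shortfall found at Day 90.** A reader might infer that withdrawal at that visit means discarding the result. The text does not require this: ACQ, FeNO and spirometry belong to the same visit, so the withdrawal evaluation would be the Day 90 evaluation. The text is only silent on how such a subject counts.
- **Overstated benefit as a fact.** The sign of the bias depends on dC − dW, which is unknown. Subjects may skip capsules because they feel well or forget, and a major deviation need not be related to outcome.
- **Missed visits.** These are given as an example of non-compliance, but the mandatory wording does not attach to them alone. Early Withdrawal also speaks generally of investigator discretion, although the three triggers quoted above are worded as firm.
- **Data that would exist.** A subject removed at Day 60 would have two post-baseline ACQ and FeNO values, and possibly a withdrawal assessment. This softens the problem for those outcomes. For FEV1 it helps only if the evaluation takes place. The design section does speak of outcome assessments at Days 30 and 60, but the visit lists include no spirometry there.

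None of this supplies a Day 90 value for a subject removed at Day 30 or 60. An on-treatment estimate is a possible choice in a small Phase II study, but it can still be obtained as a subset when everyone is followed, whereas the reverse is impossible.

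**Conclusion.** The point holds as a retention weakness. Followed as written, the plan assures Day 90 data only for subjects who stay at or above 75% compliance and have no other removal trigger, and FEV1 has the thinnest cover. This may bias the mean change, probably upward on the assumption that non-adherence tends to go with poor response. The protocol does not establish that assumption.

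For 1 to 5 removals out of 17, the bias runs from about −0.07 to +0.22 ACQ-7 points and from about −15 to +88 ml FEV1 over the responses assumed above. With one or two removals and no change in those removed, it is only 0.03 to 0.06 points. The change is worth making because it is cheap and the loss cannot be repaired afterwards.

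**What to change.** In the Early Withdrawal and Protocol violation sections:

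1. Separate stopping the product from leaving the study. The rules on who stops the product stay as written.
2. Keep every subject who took at least one dose, and who still consents, in follow-up through the Day 90 FEV1, FeNO and ACQ-7 assessments.
3. Retain the evaluation at the time of stopping as an addition to the Day 90 assessment, not a replacement for it.
4. State that a compliance shortfall found at Day 90 does not remove that visit's data.
5. Use the subset with at least 75% compliance as a sensitivity analysis. The detail can sit in the statistical analysis plan.
6. Reconcile the first-period regimen wording, so that the compliance percentage has one denominator, and the two sample sizes.

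The cost is protocol wording and a Day 90 visit for a few subjects, using assessments already in the schedule. The estimate may turn out less favourable.

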## **Study Procedures**

## **Pre-study Visit (Screening)**

At screening, a Subject Information and Consent Form will be given to the potential subject. The subject will read the information carefully and will be given the opportunity to seek more information if needed. The subject will also be provided with the option of taking the consent form home to review prior to making his or her decision. If agreeable, the subject will sign the consent form and receive a duplicate. After the subject has signed the informed consent, the screening number will be assigned sequentially and entered in the Screening and Enrolment Log. Screening numbers will be allocated in the chronological order of the subject's signing the informed consent.

#### Screening includes:

- Review of medical history and concomitant therapies.
- Symptoms examination
- Phyiscial examination
- Review of inclusion/exclusion criteria
- Exhaled nitric oxide (FENO) measurements

If  $FE_{NO}$  is > 25 ppb,

- Spirometry measurement (FEV1 and FVC)
- Laboratory tests (basic hematology and chemistry)
- Urine pregnancy test for women of childbearing potential
- ECG

#### Baseline - (Visit 1 / Week 0/ Day 0)

Subjects will receive the treatment regimen of LiGNO™ TMM.

Eligible subjects will return to the clinic in a fasted condition (last food intake at least 12 hours before the visit; subjects will be allowed to drink water) for baseline assessments:

- vitals signs, weight and height measurement
- Asthma Control Questionnaire
- review of concomitant therapies
- physical examination
- Review of spirometry measurements (FEV1 and FVC)
- Review of laboratory tests (basic hematology and chemistry)
- Review of urine pregnancy test for women of childbearing potential
- Review of baseline ECG

After all baseline assessments are reviewed, subjects will be dispensed the investigational product.

Subjects will receive LiGNO™ TMM. Subjects will be instructed in detail by site personnel about the dosing regimen. The first dose of study product is to be taken the day after the Baseline visit, treatment Day 1, consisting of :

• 2 capsules of 250 mg L. rhinocerus, once a day after breakfast and dinner daily for 4 weeks

Subjects will be given a diary card to record their symptoms every day. Subjects will be reminded to fast (12 hours) prior to their study visits. The next visit will be scheduled for Week 4/Day 30.

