#### **Rationale of Study**

#### Asthma and FeNO

Asthma is a disease with marked heterogeneity in its clinical course and in its response to treatment. Variability in the type of airway inflammation may underlie this heterogeneity. Despite treatment with inhaled glucocorticoids, many patients continue to have uncontrolled asthma that requires more intensive therapy. Based on the ethnobotanical uses of Tiger Milk mushroom in treating asthma, its significant anti-inflammatory activity and also the positive feedbacks received from asthmatic volunteers using LiGNO™ Tiger Milk Mushroom, it is worthwhile to explore the potential of Tiger Milk Mushroom to be used as an immunomodulatory treatment to support conventional therapy through a proper designed clinical study. This will allow patients with uncontrolled asthma to obtain access to a new complementary therapy which they may benefit from. The objective of the study is to investigate the efficacy of L. rhinocerus to be used as a complementary therapy in improving symptoms, preventing exacerbations and reducing underlying airway inflammation in asthma patients.

 $FE_{NO}$  (fractional exhaled nitric oxide) is the only available point of care test to assess type-2 inflammation in asthma. Raised  $FE_{NO}$  with blood eosinophilia should be regarded as treatable traits of type 2 inflammation.  $FE_{NO}$  maybe useful for providing

feedback to both physicians and patients taking asthma therapy (in particular inhaled corticosteroids, ICS) particularly when the spirometry is normal.

 $FE_{NO}$  values can be influenced by several non-disease-related factors, thus filling in a questionnaire for NO measurement is recommended. Confounding factors could be related to the patient, like genetics, sex, weight and height, diet (*i.e.*, coffee) or taking drugs such as anti-inflammatory medications; also current smoking and atopy seem to influence  $FE_{NO}$  levels. Allergen exposure is associated with higher levels of  $FE_{NO}$  but they could decrease during the early phase of allergic response. Smoking is an important determinant of  $FE_{NO}$  levels and current smokers exhibit lower levels of  $FE_{NO}$  in comparison to ex-smokers and never smokers. Both active and passive smoking have effects on lowering  $FE_{NO}$  as demonstrated in healthy adults and in both adults and children suffering from asthma, regardless their allergy status.

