 $FE_{NO}$  could be influenced also by viral respiratory infections. Age seems to be important too, especially in children, but correlation between age and sex has still to be defined. Recently, also ethnicity seems to have a role in  $FE_{NO}$  results, impacting clinical management.

Moreover, there are also technical confounding factors in  $FE_{NO}$  measurement, like the NO analyzer used, measurement technique, exhalation flow rate or nasal NO contamination. Spirometry could also influence  $FE_{NO}$  results, thus it should not be performed first.  $FE_{NO}$  could increase due to bronchodilation and it could decrease due to bronchoconstriction.

Reference values have been described for  $FE_{NO}$ . In clinical practice,  $FE_{NO}$  <25 ppb in adults is considered the normal value.  $FE_{NO}$  levels between 25-50 ppb in adults (20-35 ppb in children) should be contextualized within the clinical context.

The eosinophilic asthma phenotype is characterized by sputum eosinophils  $\geq$ 3% and identifies patients with a good response to corticosteroids and T2 immunomodulators. FENO values >50 ppb are likely connected with airway eosinophilic inflammation and this data may be used to predict a response to anti-inflammatory therapy, while low FENO <25 ppb correlates with less eosinophilic inflammation and responsiveness to corticosteroids. Diagnostic FENO cut point in well controlled asthma is usually indicated by normal values. FENO >30 ppb is usually associated with uncontrolled asthma.

According to GINA guidelines, following the diagnosis of severe asthma,  $FE_{NO} \ge 20$  ppb is considered the cut-off characterizing Type 2 inflammation severe asthma and it is used to assess this asthma phenotype, together with other markers like blood and sputum eosinophils. It has been suggested a  $FE_{NO}$  cut point of 21 ppb best fits  $\ge 3\%$  sputum eosinophils in corticosteroid-naive patients.

Very few data from studies analyzing clinically important change of  $FE_{NO}$  in individual patients is available and different are the results depending on the considered outcome. Considering simply the within-subject coefficient of variation, in healthy subject is approximately 10% (corresponding to a raw change up to 4 ppb) while it

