## d) $FE_{NO}$ of > 25 ppb measured at baseline screening.

- Absence of a recent exacerbation 6 weeks prior to enrolment
- Non-smoker patient for at least six months and with a prior tobacco consumption < 10 packs/ year

- Patient with normal organ function
- Patient weight > 41 kg and body mass index (BMI) between 18 and 35 kg/m2

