#### Investigational Study Visit (Visit 2 / Week 4 / Day 30)

Subjects will return the clinic on Week 4 (Day 30). Any remaining investigational product or empty packaging will be returned and a new supply dispensed.

Study visit assessments will include:

- vitals signs, weight measurement
- review of concomitant therapies
- review of adverse events
- review of the diary card record
- symptoms examination
- compliance calculation
- Asthma Control Questionnaire
- Laboratory tests (basic hematology and chemistry)
- Exhaled nitric oxide (FENO) measurements
- ECG

Subjects will receive LiGNO™ TMM. Subjects will be instructed in detail by site personnel about the dosing regimen. Dosing will be escalated to

• 2 capsules of 250 mg L. rhinocerus, twice a day after breakfast and dinner daily for 8 weeks

Subjects will be reminded to fast (12 hours) prior to their study visits. The next visit will be scheduled for Day 60.

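### The visit lists take the only pre-treatment FeNO at screening with no fasting condition stated, while the on-treatment readings fall at fasted visits; the Day 0 list omits the FeNO that the design section implies

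*Protocol*

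**What the plan says.** **Where FeNO is listed.** The Screening list includes "Exhaled nitric oxide (FE NO ) measurements", and inclusion criterion d) sets an entry cut of more than 25 "ppb measured at baseline screening". FeNO is listed again at Visits 2, 3 and 4 (Days 30, 60 and 90). It is absent from the Baseline (Day 0) list, even as a review item, although spirometry, laboratory tests, pregnancy test and ECG are all carried forward there for review.

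**Where fasting is required.** The screening sections are silent on fasting. The first requirement is at Baseline: "Eligible subjects will return to the clinic in a fasted condition", with no food for at least 12 hours and water allowed. The Baseline, Visit 2 and Visit 3 sections each end with a reminder for the visits that follow: "Subjects will be reminded to fast (12 hours) prior to their study visits".

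**What the design section says.** Study Design and Sample Size states that assessments for the primary and secondary outcomes take place on Days 0, 30, 60 and 90. FeNO change is a listed secondary endpoint, and the Objectives section places FeNO in the primary objective.

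**What the background says.** Asthma and FeNO lists influences on the reading: diet, with coffee as the example, "or taking drugs such as anti-inflammatory medications", and airway calibre, since FeNO "could increase due to bronchodilation and it could decrease due to bronchoconstriction". It says a questionnaire is recommended when NO is measured. No visit list contains one. Inhaler use is covered only by general items such as "Review of medical history and concomitant therapies", which do not ask for the time of the last inhalation.

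**The concern.** In a single-arm trial each subject's pre-treatment value is the only comparator, so it should be taken under the same conditions as the later values. By the visit lists it need not be: the pre-treatment reading carries no dietary condition and the later ones do. A difference in conditions that shifts readings on average would not shrink with more subjects, and no analysis could separate it from the effect of the product. What a subject had eaten or drunk is not recorded, so it could not be adjusted for afterwards either. The affected result is the FeNO change at 90 days, together with the FeNO response cut in Study Design and Sample Size (at least 20% above 50 ppb, more than 10 ppb below 50 ppb).

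**Working it through.** **Step 1: the visits side by side.**

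| Visit | FeNO listed? | Fasting condition |
|---|---|---|
| Screening | Yes (also the entry reading) | None stated |
| Day 0 | No | 12 hours, water allowed |
| Day 30 | Yes | 12 hours (reminder) |
| Day 60 | Yes | 12 hours (reminder) |
| Day 90 | Yes, before spirometry | 12 hours (reminder) |

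The one visit before treatment that has a fast has no FeNO, and the one visit before treatment that has FeNO has no stated fast. Day 0 is truly pre-treatment, because the first dose is taken the day after.

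**Step 2: does the difference bear on FeNO?** The background names diet and coffee, not fasting as such. The Day 0 fast allows water, so on a natural reading it excludes coffee as well as food. The fasting rule therefore acts on a factor that the Protocol itself lists. No size or direction is given.

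**Step 3: the conflict over Day 0.** The design section implies a Day 0 FeNO; the Baseline list omits it; criterion d) attaches the word baseline to the screening value. If the design section governs, the fasting conditions match. If the visit list governs, they may not.

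**Step 4: how large a shift would matter.** No figure in the Protocol can be reproduced on this point, and the sample size has no stated derivation. The following is a yardstick only. Input: within-subject coefficient of variation of about 20% in asthma (Asthma and FeNO). Assumptions: this value applies to single readings between visits, and change is analysed on the log scale with a paired t-test at two-sided 0.05.

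- SD of log change = √(2 × ln(1 + 0.20²)) = 0.280
- SE with 17 subjects (design section) = 0.280 / √17 = 0.068, roughly 7%
- SE with 10 subjects (Study Population section) = 0.280 / √10 = 0.089, roughly 9%

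The shift due to conditions is unknown. Over an assumed range of 0 to 20% towards lower on-treatment readings, with no treatment effect, the chance of a significant fall would be:

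| Assumed shift | n = 17 | n = 10 |
|---|---|---|
| 0% | 2.5% | 2.5% |
| 5% | 10.6% | 7.5% |
| 10% | 30.8% | 18.6% |
| 15% | 61.3% | 37.5% |
| 20% | 86.9% | 61.3% |

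A shift in the other direction is equally open and would hide a benefit: a true 10% fall is cancelled by on-treatment readings about 11% higher because of conditions (0.90 × 1.111 = 1.00). The table shows sensitivity to an assumption; it is not evidence that any such shift exists.

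**The case against.** **The text does not say screening is unfasted.** A reader might infer that the screening FeNO is taken after food. The Protocol is only silent. Unfasted is plausible, since consent is given at that visit and the first fast is for the return visit, but it remains an inference. Equally, the later fasts are reminders, with no stated check that they were kept.

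**A Day 0 reading may be intended.** If the design section governs, a fasted baseline exists and the mismatch disappears. So it would be wrong to infer that the problem exists whichever reading is named as baseline. What stands is that the Baseline list, which site staff will follow, does not contain the reading.

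**No direction is given.** A reader might infer that every subject is biased the same way, towards a false fall. The only direction in the Protocol concerns airway calibre, not food, so this is unsupported.

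**Inhaler timing.** A reader might add that uncontrolled bronchodilator use inflates the screening value. The absence of a timing record applies to all visits alike, and subjects already need regular inhaled combination therapy. The gap adds noise; it biases the change only if use differs between visits, for example if reliever use falls during treatment.

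**Existing control and weight.** The Protocol does control one confounder that it names: FeNO is listed ahead of spirometry at screening and explicitly precedes it at Day 90. FeNO change is listed as a secondary endpoint, although the Objectives section makes it primary.

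These objections narrow the point but do not remove it. Followed as written, the visit lists leave the conditions of the single-arm comparison unmatched.

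**Conclusion.** The point holds as a risk of bias that comes from an inconsistent schedule. By the visit lists, the only pre-treatment FeNO has no stated fasting condition, the on-treatment readings fall at visits with a 12-hour fast reminder, and the design section and the Day 0 list disagree on whether a Day 0 reading exists. Any effect of the differing conditions enters the before/after change and could create or hide an apparent benefit. The documents do not establish its size or direction. The yardstick of roughly 7% (17 subjects) or 9% (10 subjects) per standard error rests on the 20% variation figure and a log-scale paired analysis; it shows only that a modest common shift would not be negligible in a trial of this size. This is a cheap improvement that should be made, not a proven flaw in the result.

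**What to change.** 1. Reconcile Study Design and Sample Size, inclusion criterion d), the Screening list and the Baseline list. Preferably, add FeNO to the already fasted Day 0 visit, name that value as the baseline for the FeNO change, and keep the screening value for eligibility only. Alternatively, apply the same 12-hour fast to the screening FeNO and name that value as baseline.
2. With every FeNO reading, record last food, last coffee and time of last inhaler use, in line with the questionnaire that the background recommends. This is a record only; no inhaler rule is proposed here.
3. If spirometry is also done on Day 0, keep FeNO first, as the Protocol already does at Day 90.

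The cost is at most one extra breath test at a visit that already takes place, and a short entry on the case report form.

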#### STUDY DESIGN AND SAMPLE SIZE

This is a prospective, open-label, Phase II study. The study will consist of a single treatment phase including:

- Screening period
- 12 weeks (90 days) of treatment period.

The planned sample size for this study is 17 subjects. In order to evaluate primary and secondary outcomes, study assessments will be conducted at Day 0, 30, 60 and 90 of treatment.

The MCID for FEV1 is 12% and 200 ml measured by spirometry obtained at baseline (immediately prior to the start of the treatment) with the results obtained 2 hour after administration of study medication (2-hour postdose FEV1) after 12 weeks of treatment.

The MCID for  $FE_{NO}$  is a reduction of at least 20% in  $FE_{NO}$  for values over 50 ppb or more than 10 ppb for values lower than 50 ppb will be used as the cut point to indicate a significant response to treatment.

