#### **Inclusion Criteria**

All adults aged 18 years and above with a prior documented diagnosis of atopic (Th2driven) asthma by a physician based on Global initiative for Asthma (GINA) 2020 Guidelines whose asthma is uncontrolled on ICS/LABA combination therapy based on the following criteria:

- a) A well documented requirement for regular treatment with a minimum dose of either fluticasone /salmeterol combination therapy or budeosnide/formoterol combination therapy in the 12 months prior to screening with or without maintenance of oral corticosteroids (OCS).
- b) Forced expiratory volume (FEV1) > 50% to <80% predicted normal during the screening phase (3 attempts maximum) and on the randomization day prior to the first dose of IMP.
- c) Reversibility of at least 12% and 200 ml in FEV1 after 200 ug to 400 ug (2 to 4 inhalations) of salbutamol during the screening phase (3 attempts maximum), or documented history of reversibility test that met these criteria within 12 months prior to screening.

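### The visit schedule makes the qualifying FeNO reading the baseline and contradicts the protocol's own pre-dose spirometry, so a modest regression to the mean is counted as treatment effect

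*Protocol*

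**What the plan says.** **What is promised for Day 0.** Protocol, Study Design and Sample Size: for the primary and secondary outcomes, "study assessments will be conducted at Day 0, 30, 60 and 90 of treatment". The same section takes spirometry for the FEV1 threshold as "obtained at baseline (immediately prior to the start of the treatment". Inclusion criterion b) requires FEV1 between 50% and 80% predicted both in screening, with up to three attempts, and "on the randomization day prior to the first dose of IMP".

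**What is scheduled.** Screening lists "Exhaled nitric oxide (FE NO ) measurements", and the remaining screening tests follow only if the result is above 25 ppb. Inclusion criterion d) requires FeNO "of > 25 ppb measured at baseline screening". The Visit 1 list has no FeNO item, measured or reviewed. For lung function it has "Review of spirometry measurements (FEV 1 and FVC". It also states: "The first dose of study product is to be taken the day after the Baseline visit". FeNO next appears at Visit 2 (Day 30). Spirometry next appears at Visit 4 (Day 90).

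**Role of the two measures.** Change in mean trough FEV1 is a primary endpoint. Change in mean FeNO in ppb is listed as a secondary endpoint, but FeNO is also named in the primary objective. The study is open-label with one arm.

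**The concern.** Patients enter because one noisy FeNO reading was above a cut-off. Some readings were above it partly by chance, and their next reading is lower on average whether or not the product works. If the same reading is then the baseline for the Day 90 change, that fall is credited to treatment. There is no control arm to remove it, and a larger sample only estimates the biased quantity more precisely.

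For FEV1 the protocol gives two different baselines. Under the Visit 1 list, the baseline is the screening value that qualified the patient. Under the design section and criterion b), it is a new pre-dose value. Sites could follow either, so baselines might differ between patients in a very small study. The reference to a randomization day adds to the uncertainty, because nothing is randomised.

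There is also a smaller mismatch. Visit 1 and later visits call for a 12-hour fast, but screening states none, and the rationale lists diet among the influences on FeNO. The direction of that effect is unknown.

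ACQ-7 is not exposed in the same direct way: it is collected at Visit 1 and has no entry cut-off.

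**Working it through.** **1. Which readings exist before the first dose, by visit list**

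| | Screening | Visit 1 (Day 0) | First dose (Day 1) | Next reading |
|---|---|---|---|---|
| FeNO | measured, must exceed 25 ppb | not listed | – | Day 30 |
| Spirometry | measured, 50–80% window | reviewed only | – | Day 90 |
| ACQ-7 | not listed | measured | – | Day 30 |

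The screening and Visit 4 lists name spirometry as a measurement, without the word review, so the natural reading of Visit 1 is that it looks back to screening. The protocol states no figure on this point that could be reproduced.

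**2. FeNO: expected fall with no treatment effect**

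From the protocol: cut-off 25 ppb; within-subject coefficient of variation about 20% in asthma (Rationale); n = 17.

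Assumed, because the protocol does not give them: log-normal true levels, median M = 20 to 40 ppb and geometric SD (GSD) 1.6 to 2.0 among screened patients; independent errors between visits; a paired t-test at two-sided 5%.

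Formulas:
- within-subject log variance sw² = ln(1 + 0.20²) = 0.0392, so sw = 0.198
- total log SD st = √(sb² + sw²), with sb = ln(GSD)
- c = ln(25/M)/st
- expected log fall = (sw²/st) × φ(c)/(1 − Φ(c))

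Worked case, M = 20, GSD 1.6: sb = 0.470; st = 0.510; c = 0.2231/0.510 = 0.438; φ(c)/(1 − Φ(c)) = 1.096; log fall = 0.0392/0.510 × 1.096 = 0.084, a fall of 8.1%.

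Worked case, M = 40, GSD 2.0: sb = 0.693; st = 0.721; c = −0.652; ratio = 0.434; log fall = 0.0392/0.721 × 0.434 = 0.024, a fall of 2.3%.

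Simulation with no effect gives the raw-scale falls and the share of 17-patient trials with a significant fall (nominal 2.5%):

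| Median, GSD | Mean fall, ppb | Mean fall, % | Geometric fall, % | Significant, raw | Significant, log |
|---|---|---|---|---|---|
| 20, 1.6 | 2.1 | 5.8 | 8.1 | 15% | 22% |
| 30, 1.6 | 1.2 | 2.7 | 4.4 | 6% | 9% |
| 40, 2.0 | 0.6 | 1.0 | 2.3 | 3% | 5% |

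With an independent Day 0 reading as baseline, the mean change is zero within simulation error and the rate returns to 2–3%.

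Sensitivity: with a narrower source (median 20, GSD about 1.35) the geometric fall is 12.6%, the mean fall 3.3 ppb and the log-scale rate about 50%. If the variation between readings 90 days apart were 30% instead of 20%, the geometric fall would be 4.9% to 21.3% over medians of 20 to 40 ppb and between-patient log SDs of 0.3 to 0.7.

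**3. FEV1, only if the Visit 1 list governs**

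Assumed: between-patient SD 12 to 15 points and within-patient SD 4 to 6 points of percent predicted; the first reading inside 50–80% in one to three attempts is the baseline.

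| Source mean, % predicted | Null change, points |
|---|---|
| 60 | −0.3 to −0.9 |
| 65 | 0 |
| 70 | +0.3 to +1.0 |
| 80 | +0.7 to +2.8 |

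At an assumed predicted FEV1 of 3 L, one point is 30 ml, so the range is about −0.94 × 30 = −28 ml to +2.82 × 30 = +85 ml, against the protocol's 200 ml threshold. The sign changes because the window is two-sided. If the window is applied again to a fresh Day 0 value and that value is the baseline, roughly half to 60% of the effect remains.

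**The case against.** The strongest reply is that the effect is small, and smallest where the protocol points. The rationale links uncontrolled asthma with FeNO above 30 ppb. At medians of 30 to 40 ppb the mean fall is only 0.6 to 1.2 ppb (1.0% to 2.7%), with significant falls in about 3% to 6% of null trials on the raw scale. The upper end of the range needs a source population in which only about a third of those screened would qualify. The endpoint is mean FeNO in ppb, so the log-scale figures and the paired t-test describe an analysis the protocol does not state. All of this is fair. It limits the size of the bias, not its existence or direction.

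It can also be said that the general Day 0 sentence and criterion b) show an intention to measure on Day 0, and that the Visit 1 review could include a spirometry reading taken under criterion b). That may be so for FEV1, but then the passages need to agree. For FeNO, the itemised list that sites follow contains nothing to review or measure. An analysis plan cannot supply a reading that no visit collects.

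Finally, a Day 0 reading does not make the study controlled. Time trends and better adherence to background therapy would still be confounded with treatment. This stands: the change removes only the part caused by selection.

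**Conclusion.** The concern holds. By the visit schedule, the FeNO baseline is the reading that qualified the patient. The resulting bias favours the product whatever the source population, and a larger sample does not remove it. Its size is modest: 0.6 to 2.1 ppb over the main set of assumptions, well short of the protocol's response rule (a 20% fall from values above 50 ppb, or more than 10 ppb from lower ones). It is still enough to raise the chance of a spurious significant fall above its nominal level. The magnitude depends on the assumed median and spread of FeNO among screened patients, neither of which is in the protocol, and could be larger than the main range. The direction does not depend on them.

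For FEV1, the secure finding is the contradiction between the design section, inclusion criterion b) and the Visit 1 list. Any bias there could go either way and is below the 200 ml threshold in every case examined. The point should be corrected before enrolment, because a pre-dose reading cannot be recovered later.

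**What to change.** - Add FeNO, followed by spirometry, to the Visit 1 list, both before product is dispensed. The order follows the rationale, which says of spirometry "thus it should not be performed first".
- Define these Visit 1 values as the analysis baseline for FeNO and FEV1.
- Use the screening FeNO for eligibility only, and do not apply the 25 ppb cut-off again on Day 0; doing so would bring the selection back.
- Reconcile the design section, inclusion criterion b) and the Visit 1 list on pre-dose spirometry, and replace the reference to a randomization day with Day 0. Since the first dose falls the day after Visit 1, the baseline definition in the design section should say so.
- If the FEV1 window is applied to the Day 0 value, state that part of the selection effect (about half to 60% under the assumptions above) remains in the FEV1 change.

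The cost is one extra breath test per patient at an existing visit. Pre-dose spirometry on that day is already called for by criterion b). It also places the FeNO baseline under the same fasting condition as later visits. The observed FeNO improvement will probably be slightly smaller, and time effects unrelated to selection will still need to be acknowledged as a limit of the single-arm design.
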